10.2. Cumulative Dose

For RT, cumulative dose is defined as the dose given across the treatment period in Gy.

Radiotherapy consists of a conventionally fractionated regimen delivering a total dose of 60 Gy in 30 fractions in 6 weeks, a fraction of 2 Gy once daily, 5 days per week.

For chemotherapy, cumulative dose is defined as the sum of all doses taken across the treatment period in mg or mg/m².

Doses for TMZ

Dose modifications for TMZ follow the standard of care at the institution.

Doses for MRZ

Acceptable MRZ dose reductions are as follows:

Dose Level	Weekly dose	Concomitant Treatment Schedule	Adjuvant Treatment Schedule
Starting dose	0.8 mg/m ²	Days 1, 8, 15, 29, 36	Days 1, 8 and 15 (28-day cycle)
Dose level – 1	0.7 mg/m ²	Days 1, 8, 15, 29, 36	Days 1, 8 and 15 (28-day cycle)
Dose level – 2	0.55 mg/m ²	Days 1, 8, 15, 29, 36	Days 1, 8 and 15 (28-day cycle)
Dose level – 3	0.4 mg/m ²	Days 1, 8, 15, 29, 36	Days 1, 8 and 15 (28-day cycle)

10.3. Dose Intensity

Dose intensity during the treatment is defined as the cumulative dose divided by the treatment duration. Dose intensity will be calculated separately for TMZ and MRZ.

The dose intensities of TMZ and MRZ per subject are defined separately for the concomitant and the maintenance phase. The dose intensities will be calculated as:

Dose Intensity_{Conc}

$$= \frac{\text{Cumulative dose of Conc TMZ/MRZ from 1st administration until end of RTX } \left(\frac{\text{mg}}{\text{m}^2}\right)}{\text{Treatment duration (weeks)}}$$

Dose intensity_{Main}

$$= \frac{\text{Cumulative dose of Main TMZ/MRZ since start of 1st maintenance TMZ cycle } \left(\frac{\text{mg}}{\text{m}^2}\right)}{\text{Treatment duration (weeks)}}$$

10.4. Relative Dose Intensity

Relative dose intensity is the dose intensity divided by the planned dose intensity.

The planned dose intensity is

$$\begin{aligned} & \text{Planned dose intensity}_{\text{Conc TMZ or MRZ}} \\ &= \frac{42 * 75 \frac{\text{mg}}{\text{m}^2} \text{ of TMZ or } 5 * 0.8 \frac{\text{mg}}{\text{m}^2} \text{ of MRZ}}{\text{Theoretical duration of one cycle (weeks)} = 6 \text{ weeks}} \end{aligned}$$

$$\begin{aligned} & \text{Planned dose intensity}_{\text{Main TMZ}} \\ &= \frac{(150 \frac{\text{mg}}{\text{m}^2} \text{ at cycle 1} + \sum_1^N (n - 1) * 200 \frac{\text{mg}}{\text{m}^2}) / N \text{ of TMZ}}{\text{Theoretical duration of one cycle (weeks)} = 4 \text{ weeks}} \end{aligned}$$

$$\begin{aligned} & \text{Planned dose intensity}_{\text{Main MRZ}} \\ &= \frac{3 * 0.8 \frac{\text{mg}}{\text{m}^2} \text{ of MRZ}}{\text{Theoretical duration of one cycle (weeks)} = 4 \text{ weeks}} \end{aligned}$$

Relative dose intensities will be categorized into < 60%, 60% to <80%, 80% to <90%, 90% to <110%, and \geq 110%, and frequency counts will be provided by treatment arm.

For RT, the (relative) dose intensity is not meaningful. The number of subjects with cumulative dose >90%, \leq 90% of the planned total dose (60 Gy) will be summarized by treatment arm.

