## 5.1.2 Temozolomide

Temozolomide (TMZ) is an approved drug for the treatment of patients with newly diagnosed glioblastoma. TMZ is available commercially and will therefore be taken off the shelf.

During radiotherapy, TMZ is administered at a dose of 75 mg/m^2 daily, starting at the first day of radiotherapy, typically for 42 days and for a maximum of 49 days. Four weeks after the last day of radiotherapy, treatment with TMZ is resumed at a dose of 150 mg/m^2 (cycle 1) and 200 mg/m^2 (subsequent cycles) daily for 5 days every 28 days (corresponding to a cycle) for up to 6 cycles. TMZ will be administered and prescribed according to the official label and the standard of care which has been defined in a previous EORTC/NCIC trial (Ref. 42).

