10.1. Treatment Duration

Radiotherapy

Radiotherapy consists of a conventionally fractionated regimen delivering a total dose of 60 Gy in 30 fractions in 6 weeks, a fraction of 2 Gy once daily, 5 days per week. The RT duration (in weeks) is defined as $(\text{last RT dose date} - \text{first RT dose date} + 1) / 7$.

Chemotherapy

The treatment start date is the date of the first dose of study drugs (MRZ or TMZ). The treatment end date is the date on which the decision was made by investigator to discontinue subject's treatment. Whenever the treatment is given in cycles and the last planned day of treatment is not the last day of the cycle, the total duration of the treatment must account for this by adding the appropriate number of days to complete the last cycle.

Temozolomide is given on a daily basis for 6 weeks during RT (concomitant phase) and after a 4-week interval, TMZ is given on days 1-5 of a 28-day cycle (maintenance phase).

- The concomitant TMZ duration (in weeks) is defined as $(\text{last concomitant TMZ dose date} - \text{first concomitant TMZ dose date} + 1) / 7$.
- The maintenance TMZ duration (in weeks) is defined as $([\text{maintenance TMZ end date} - \text{maintenance TMZ start date}] + 1 + (28 - n)) / 7$ where n is the last day of administration of the last cycle, ie, Day 1, 2, 3, 4, or 5.

Marizomib is given on Days 1, 8, 15, 29, 36 for one cycle of 6 weeks during radiotherapy (concomitant phase) and after a 4-week interval, MRZ is given on days 1,8,15 of a 28-day cycle (maintenance phase).

- The concomitant MRZ duration (in weeks) is defined as $([\text{last concomitant MRZ end date} - \text{first concomitant MRZ start date}] + 1 + (42 - n)) / 7$.
- The maintenance MRZ duration (in weeks) is defined as $([\text{maintenance MRZ end date} - \text{maintenance MRZ start date}] + 1 + (28 - n)) / 7$, where n is the last day of administration of the last cycle, ie, Day 1, 8, or 15.

For subjects who are still on treatment at the time of study closure or clinical cutoff, the planned cycle length will be used to calculate the end date and for both drugs the treatment duration (in weeks) is defined as: $[\text{the study treatment end date} - \text{the first study drug start date} + 1] / 7$.

Descriptive statistics will be provided for treatment duration and total number of cycles by treatment arm.

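### SAP 10.4's planned maintenance temozolomide dose intensity, as printed, omits the five daily doses per cycle and leaves n and N undefined, so a fully compliant 6-cycle patient does not read 100%

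*SAP*

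**What the plan says.** SAP 10.4 divides each patient's dose intensity by a planned dose intensity. For concomitant TMZ, concomitant marizomib (MRZ) and maintenance MRZ, the planned numerators are 42 × 75, 5 × 0.8 and 3 × 0.8 mg/m², each a number of doses times a dose. For maintenance TMZ the numerator is 150 mg/m² "at cycle 1} + \sum_1^N (n - 1) * 200" mg/m², divided by N, over a 4-week cycle.

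The delivered side is built from all doses. In SAP 10.2, "cumulative dose is defined as the sum of all doses taken across the treatment period"; in SAP 10.3, "Dose intensity during the treatment is defined as the cumulative dose divided by the treatment duration". On the schedule, SAP 10.1 says "TMZ is given on days 1-5 of a 28-day cycle (maintenance phase"), and Protocol 5.1.2 gives 150 mg/m² in cycle 1 and 200 mg/m² in later cycles, "daily for 5 days every 28 days (corresponding to a cycle) for up to 6 cycles".

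SAP 10.4 does not define n or N. The n used for maintenance TMZ in SAP 10.1 is a dosing day: "where n is the last day of administration of the last cycle, ie, Day 1, 2, 3, 4, or 5".

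The results are tabulated by arm: "Relative dose intensities will be categorized into < 60%, 60% to <80%, 80% to <90%, 90% to <110"%, with a top row of 110% or more. SAP 3 places all of section 10 in both the primary and the long-term follow-up reports.

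**The concern.** The ratio compares five daily doses per cycle in its numerator with one per cycle in its denominator. Because the sum is unindexed and its symbols are undefined, two programmers could code different formulas and both claim to follow the SAP.

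The table has a real use. TMZ is the backbone of both arms, and Protocol 1.2.1 reports that the data monitoring committee saw severe neurological and other grade 3-4 toxicity with marizomib. Readers will ask whether TMZ delivery held up in the marizomib arm. The relative dose intensity categories by arm are one of the places where they will look.

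**Working it through.** **Inputs.** Doses and schedule are from Protocol 5.1.2 and SAP 10.1. Delivered intensity is cumulative dose over duration (SAP 10.2, 10.3). Maintenance TMZ duration is (end − start + 1 + (28 − n))/7 weeks, with n the last dosing day (SAP 10.1). The patient is assumed to take every planned dose without delay, and the end date is taken as the last dosing day.

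**1. The three neighbouring formulas, as a calibration.**
- Concomitant TMZ: planned 42 × 75/6 = 525; delivered 3150/6 = 525; ratio 100%.
- Concomitant MRZ: planned 5 × 0.8/6 = 0.667; duration (36 + 6)/7 = 6 weeks; delivered 4.0/6 = 0.667; ratio 100%.
- Maintenance MRZ, 18 cycles: planned 3 × 0.8/4 = 0.6; delivered 43.2 mg/m² over (17 × 28 + 15 + 13)/7 = 72 weeks = 0.6; ratio 100%.

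So the method in 10.1 to 10.4 returns 100% for full compliance when the dose count is present.

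**2. Delivered maintenance TMZ, 6 cycles.** The dose is 5 × 150 + 5 × 5 × 200 = 5750 mg/m². The last dose falls on day 5 × 28 + 5 = 145, so the duration is (145 + 23)/7 = 24 weeks. The intensity is 5750/24 = 239.58 mg/m²/week.

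**3. Planned value from the printed formula at N = 6** (each numerator divided by 6 × 4 = 24):

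| Reading of the sum | Numerator | Planned | Relative dose intensity |
|---|---|---|---|
| 200 × (N − 1), apparent intent | 150 + 1000 | 47.92 | 500% |
| n a running index from 1 to N | 150 + 15 × 200 | 131.25 | 182.5% |
| n = N inside the sum | 150 + 6 × 5 × 200 | 256.25 | 93.5% |
| n = 5 from SAP 10.1, summed | 150 + 6 × 4 × 200 | 206.25 | 116.2% |
| n = 5 from SAP 10.1, not summed | 150 + 4 × 200 | 39.58 | 605.3% |

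**4. Effect on the categories.** Under the apparent intent the ratio is 5 times too large at every N. The top row is therefore reached at 110/5 = 22% of plan. With a running index at N = 6 it is reached at 110/1.825 = 60.3% of plan.

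**5. Inserting the 5 alone is not enough.** With the sum left as printed, the running-index reading gives 182.5/5 = 36.5% and the n = N reading gives 93.5/5 = 18.7%. The sum has to be rewritten as well.

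**6. Corrected formula.** A compliant patient receives 5 × [150 + 200 × (N − 1)] mg/m² over 4N weeks. Setting the planned intensity to 5 × [150 + 200 × (N − 1)]/(4N) therefore gives 100% at every N; at N = 6 it is 5750/24 = 239.58.

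**The case against.** **It could be an extraction fault.** The formula was read from a PDF by a program, and an index could have been lost. That is a fair caution for the sum. A lost factor of 5 is less likely, because the multipliers in the neighbouring formulas survived. It is not excluded, so the source page should be checked first.

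**The intent is plain and the effect small.** A table full of values near 500% would be noticed, and the SAP's own components show the repair. The formula feeds one derived descriptive variable; cycle counts, cumulative dose and absolute dose intensity (SAP 10) and dose reductions and delays (SAP 10.5) do not use it. All of this stands and limits the weight of the point. It does not make the printed rule correct, and a value such as 93.5% or 116.2% would not stand out on an output check.

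**Stronger readings that the documents do not support.**
- A reader might infer that the values are wrong at every number of cycles under any interpretation. They are not. With n = 5 summed, N = 2 gives (150 + 2 × 4 × 200)/8 = 218.75 against a delivered 1750/8 = 218.75, exactly 100%. With n = N, a compliant 6-cycle patient lands in the correct 90% to <110% row, though by coincidence.
- A reader might infer that arm comparisons must be biased. Under the apparent intent the factor is constant, so ratios between arms are preserved; what is lost is the meaning of the categories.
- A reader might infer from SAP 10.1, "The treatment end date is the date on which the decision was made by investigator to discontinue" treatment, that maintenance durations are overstated. But the same section says that the days added are those needed to complete the last cycle, which points to whole cycles. Only the wording of the end date needs tidying.
- A patient kept at 150 mg/m² who reads below 100% shows no defect: the formula already takes 150 then 200 as its reference.

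**Conclusion.** The printed rule is wrong and should be corrected. At the full planned course of 6 cycles, the five readings tried give 500%, 182.5%, 93.5%, 116.2% and 605.3% where 100% is due. Under the most natural reading the error is a constant factor of 5, and the category table by arm would say almost nothing. This rests on the formula as extracted, on full compliance without delays, and on the end date being the last dosing day.

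The reach is narrow: the maintenance TMZ relative dose intensity rows in two descriptive reports. Overall survival, progression-free survival, cumulative dose, cycle counts and dose reductions are unaffected.

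**What to change.** 1. Check the formula in the source PDF for lost symbols.
2. In SAP 10.4, replace the planned maintenance TMZ intensity by 5 × [150 + 200 × (N − 1)]/(4N) mg/m²/week. Define N as the number of maintenance TMZ cycles started. The SAP does not define N, so that definition is a proposal. The formula uses only the SAP's own doses and its days 1-5 schedule; it sets an analysis reference and changes no treatment.
3. Produce, or rerun if already produced, the maintenance TMZ relative dose intensity rows in the primary and long-term follow-up reports.
4. As a minor clarification, state in SAP 10.1 that the end date in the maintenance duration formulas, for both TMZ and MRZ, is the last dosing day. This agrees with the instruction there to complete the last cycle.

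The cost is one formula, one definition, one sentence and a rerun of a few table rows. No new data are needed.

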10.5. Dose Reduction/Interruption/Delay

For RT, temporary treatment interruption and/or premature discontinuation will be summarized by treatment. The number of subjects who have at least one day of temporary interruption and/or who prematurely discontinued, the number of days of temporary interruption and the reason for temporary interruption and/or premature discontinuation will be summarized by treatment arm.

For chemotherapy, dose reduction/interruption/delay will be summarized by treatment arm. The number of subjects who have at least one dose reduction/interruption/delay, number of dose reductions/interruptions/delays per subject, cycle of the first dose reduction/interruption/delay and reason for dose reduction/interruption/delay will be summarized by treatment arm.

11. Efficacy Analysis

All efficacy evaluations will be conducted using the ITT population. If the percentage of subjects excluded from PP is larger than 10% in at least one treatment arm, supportive analyses of OS and PFS using the PP population will be conducted.

[figure not shown]
Statistical comparisons will be made between the MRZ and control arms. Efficacy results that will be considered statistically significant after consideration of the strategy for controlling the family-wise Type 1 error rate are described in Section 11.1, Multiplicity. All statistical tests will be one-sided at the significance levels defined below, and the corresponding p-values and two-sided CIs for intended point estimates will be reported.

The clinical database stratification variables will not be used to perform the stratified statistical test, the one recorded by the randomization system will be used instead.

11.1. Multiplicity

For the primary endpoint OS, the formal statistical testing is based on comparisons between the MRZ and control arms in both ITT population and the uMGMT stratum. We will use a graphical method to control overall Type 1 error at one-sided 2.5%, 1.5% significance in the ITT population and 1% significance in uMGMT. If one of them is significant, we will attribute the assigned alpha to the other. We will analyze other endpoints at exploratory two-sided 5% significance.

Figure 1: Type One Error Rate Control Strategy

* The alpha for testing will be dynamically determined based on the alpha propagation strategy as illustrated by the graph above.

11.2. Analysis of Primary Efficacy Endpoint

Overall survival is the primary efficacy endpoint defined as the number of days from date of randomization to the date of death due to any cause (the date of death or censoring - date of randomization + 1). If a subject has not died, the data will be censored at the last date documented to be alive.

In the primary analyses, differences in OS between the treatment groups will be assessed by a stratified LogRank test adjusted for the stratification factors assessed at randomization (except institution), testing the null hypothesis (H0):

- H0: $HR_{MRZ \text{ arm/control arm}} = 1$

Versus the alternative hypothesis (H1)

- H1: $HR_{MRZ \text{ arm/control arm}} < 1$

The IDMC declared that there was no evidence that marizomib provides a benefit in OS

In the primary analysis of OS, the above Type One Error Rate Control Strategy (section 11.1) will be applied.

In the long-term follow-up analysis of OS, the comparison will be performed at 2-sided significance level $\alpha=0.05$ in the ITT and in each MGMT methylation status.

The primary analysis will be performed with the number of deaths in the ITT population at the time of the new database lock.

The long-term follow-up analysis will take place after 488 deaths in the ITT population and 320 uMGMT deaths have occurred.

The HR (including two-sided 95 % CI) of the MRZ group over the control group will be calculated by Cox's proportional hazards model stratified by the stratification factors assessed at randomization (except institution) in the ITT population. Assumptions underlying the Cox Proportional Hazard regression model will be checked using the ASSESS statement of PROC PHREG, based on the graphical and numerical methods (Lin D., 1993). If a severe deviation from proportional treatment hazards is detected (e.g., crossing hazards) this will be taken into account in the clinical interpretation of the treatment effect but no other measure of effect (e.g, restricted mean) or significance test will be computed.

Kaplan-Meier survival curves (product-limit estimates) will be presented by treatment group, in the ITT population and by MGMT methylation status, together with a summary of associated statistics (median survival time, 6-, 12-, 18-, 24-month OS rate estimates and estimates for every 6 months thereafter as applicable) including the corresponding two-sided 95% confidence

intervals (calculated by Greenwood formula's estimation of the standard deviation for rates and by Brookmeyer and Crowley technique for the median).

Unstratified Cox's proportional hazards model will be fitted for each subgroup defined in section 11.5 in the ITT population only. Forest Plot will be displayed with a subgroup by treatment interaction test.

All secondary analyses will be performed at 2-sided significance level $\alpha=0.05$ for exploratory purpose.

The originally planned re-randomization test will not be performed as further to the review by the IDMC, there was no evidence that marizomib provides a benefit in overall survival and by consequence no significant result had to be validated with a re-randomization test.

11.3. Analyses of Secondary Efficacy Endpoints

The secondary efficacy endpoints will be analyzed based on ITT population and by MGMT methylation status.

11.3.1. Progression-free Survival

Progression-free survival will be defined as the number of days from date of randomization to the date of earliest disease progression based on Response Assessment in Neuro-Oncology (RANO) criteria (as determined by the Investigator) or to the date of death due to any cause, if disease progression did not occur (the date of progression or death or censoring - date of randomization + 1). Subjects for whom neither death nor progression have been documented will be censored at the date of the last radiological assessment that the subject was progression-free. If a subject has no post-baseline radiological assessment, then the data will be censored at the date of randomization.

Subjects with two or more missing assessments prior to a visit with documented disease progression (or death) will be censored at the last assessment where the subject was documented to be progression free. Subjects who received new anti-cancer therapy or cancer-related surgery prior to progression or death will not be censored at the last assessment where the patient was documented as progression free prior to the new anti-cancer therapy or cancer-related surgery. Censoring rules are documented in section 15.2.

The following PFS analyses will be performed at 2-sided significance level $\alpha=0.05$ for exploratory purpose. The stratified LogRank test will be applied on the PFS time to test for differences between the 2 treatment groups. The Cox's proportional hazards model stratified by the stratification factors assessed at randomization (except institution) will provide the HR (including 95% CI). Summary of associated statistics for each treatment arm (median PFS time, 6-, 12-, 18-, 24-month PFS rate estimates and estimates for every 6 months thereafter as applicable) will be displayed with 95% CI computed using the same methods as for OS, and the Kaplan-Meier curve for PFS will be presented.

Progression-free survival Kaplan-Meier estimates will be calculated and unstratified Cox's proportional hazards model will be fitted for each subgroup defined in Section 11.5 in the ITT population only. Forest Plot will be displayed with a subgroup by treatment interaction test.

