### 6.2.2 During TMZ maintenance ± MRZ

The following assessment should be done before every cycle start (within 3 days before)

- physical examination (including weight)
- Karnofsky Performance Status (KPS) scale (Appendix E)
- vital signs (heart rate, temperature, blood pressure)
- concomitant medications and procedures
- adverse events
- hematology as in section 6.1
- biochemistry as in section 6.1
- For WOCBP, urine or serum pregnancy tests

At Cycle 1 marizomib arm only, pharmacokinetics.

\* At Cycle 1 D 1 (first day of the first adjuvant cycle): first blood sample for pharmacokinetics immediately after end of MRZ infusion and second sample within 45 minutes after end of MRZ infusion.

\* At Cycle 1 D 8: sample within 45 minutes after end of MRZ infusion.

At Cycle 2 Day 1 marizomib arm only

- a 12-lead ECG within 15 minutes after end of MRZ infusion.

Every 8 weeks (± 7 days)

- Brain MRI scans. The first scan should occur 4 weeks post end of RT. The 8-week imaging schedule will start after this scan.  
All scans are to be uploaded on the EORTC imaging platform. For detailed acquisition parameters, see the study specific imaging guidelines.

Every 12 weeks ( $\pm$  7 days) after start of maintenance phase

- translational research:
  - Mandatory: 10 mL blood draw for plasma and 10 mL blood draw for serum
  - Optional: 10 mL blood draw for extracellular vesicles and 20 mL for PBMC

Every 16 weeks ( $\pm$  7 days)

- MMSE and Quality of life assessment (modified EORTC QLQ C30/BN20)

Every 24 weeks ( $\pm$  7 days)

- For participating centers, tests of objective neurocognitive function: HVLT-R, Trail Making Tests Part A & B and COWA and the MOS questionnaire on self-perceived neurocognitive function (Appendix J)

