## 7.1.3 Progression Free Survival

Progression Free Survival (PFS): PFS is defined as the number of days from date of randomization to the date of earliest disease progression based on Response Assessment in Neuro Oncology (RANO) criteria (as determined by the Investigator) or to the date of death due to any cause, if disease progression does not occur. Patients for whom neither death nor progression have been documented will be censored on the date of the last radiological assessment that the patient was progression-free. If a patient with no post-baseline radiological assessment then the data will be censored at the date of randomization. Patients with two or more missing response assessments prior to a visit with documented disease progression (or death) will be censored at the last visit where the patient was documented to be progression free. Patients who received new anti-cancer therapy or cancer-related surgery prior to progression or death will not be censored at the last assessment where the patient was documented as progression free prior to the new anti-cancer therapy or cancer-related surgery. Detailed censoring rules will be documented in the SAP.

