## **2. Guidelines for study assessments**

### **2.1 With respect to study imaging procedures:**

For the baseline study imaging procedures, the protocol requirements have to be fully met.

For on-study imaging procedures, it is preferred that the patient have imaging performed at the investigative site as directed in the protocol.

If difficulties are encountered to perform the imaging as per the protocol, there are several possibilities, in order of preference:

Have the imaging performed offsite, locally according to the protocol-specified timing. Guidance should be given by the site to the local imaging facility about conducting scans according to all applicable requirements (modality etc. as per 1709 Imaging Guidelines).

Have the imaging performed at the site but delayed to a significant extend (a window of 2 weeks instead of 1 week will be allowed) due to travel restriction/safety of the participant.

Have the imaging performed offsite but delayed (a window of 2 weeks instead of 1 week will be allowed) due to travel restriction/safety of the participant.

Skip the imaging only if impossible to perform due to travel restriction/safety.

**For all above situations, site needs to report this in the comment fields of the applicable CRFs as well as in the Source Data.**

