15.2. Censoring Rules for PFS

Situation	Date of Progression or Censoring	Situation/Outcome
No baseline assessments and alive after 2 scheduled assessments	Randomization	Censored
Death within the first two scheduled assessments without any adequate assessment	Date of death	Event
Death between adequate assessments	Date of death	Event
No progression	Date of last adequate assessment with evidence of no progression	Censored
Study discontinuation for reasons other than disease progression or death	Date of last adequate assessment with evidence of no progression	Censored
New anti-cancer therapy or cancer-related surgery prior to progression or death	Date of last adequate assessment after start of new anti-cancer therapy or cancer-related surgery with evidence of progression prior	Event
	Date of last adequate assessment after start of new anti-cancer therapy or cancer-related surgery with evidence of no progression	Censored
Death or progression after an extended lost-to-follow-up time (two or more missed scheduled assessments)	Date of last adequate assessment with evidence of no progression	Censored

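### The PFS missed-assessment censoring rule is a cumulative count in SAP 11.3.1 and Protocol 7.1.3 but points to a gap in SAP 15.2, so one patient can be an event or censored depending on which text is programmed

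*SAP*

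**What the plan says.** Three places state the rule.

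- **SAP 11.3.1:** "Subjects with two or more missing assessments prior to a visit with documented disease progression (or death) will be censored at the last assessment" at which the subject was progression-free. The paragraph closes with "Censoring rules are documented in section 15.2".
- **Protocol 7.1.3:** "Patients with two or more missing response assessments prior to a visit with documented disease progression (or death) will be censored at the last visit" documented as progression-free. It adds "Detailed censoring rules will be documented in the SAP".
- **SAP 15.2, last row:** "Death or progression after an extended lost-to-follow-up time (two or more missed scheduled assessments") is censored at the last adequate assessment without progression. Another row of the same table, "Death between adequate assessments", counts as an event on the date of death.

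On the schedule, Protocol 6.2.2 says "The first scan should occur 4 weeks post end of RT. The 8-week imaging schedule will start after this scan". After treatment and before progression, Protocol 6.3.2.1 accepts either standard-of-care MRI or the 8-week schedule. Appendix L, section 2.1, permits a scan to be omitted during the pandemic: "Skip the imaging only if impossible to perform due to travel restriction/safety".

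SAP 5.2.2 lists PFS as the key secondary endpoint, and SAP 11.3.1 tests it at two-sided 5% for exploratory purposes. Duration of response is measured in the same way as PFS (SAP 11.3.2, Protocol 7.1.4.3).

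**The concern.** The usual reason for such a rule is that after a long unobserved gap the date of progression is poorly known. A cumulative count does not isolate that situation. It also catches patients whose progression is dated to within one regular 8-week interval, because two earlier scans were missed at unrelated times.

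Two consequences would follow if the count were programmed as worded. First, the chance of two scattered misses grows with the number of scans, so the rule would fall mainly on patients followed longest. Second, those patients would be censored at the scan just before a known event, which pushes the late part of the PFS curve upward. SAP 11.3.1 asks for PFS rates at 6, 12, 18 and 24 months and every 6 months thereafter, and the long-term follow-up analysis will contain more scans per patient. Duration of response would inherit the same rule.

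**Working it through.** **1. The texts side by side.** Take a patient with scan 1 done, 2 missed, 3 done, 4 missed, 5 done without progression, and 6 showing progression.

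| Text | Test applied | Result |
|---|---|---|
| SAP 11.3.1, Protocol 7.1.3 | Two misses before the progression visit: yes | Censored at scan 5 |
| SAP 15.2, read as a gap | Event follows a prolonged loss to follow-up: no, scan 5 was adequate | Event at scan 6 |
| SAP 15.2, bracket read alone | Two missed scheduled assessments: yes | Censored at scan 5 |

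The outcome depends on which wording the programmer follows.

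**2. Inputs for the size.** The plan states no figure to reproduce here: no miss rate, no median PFS and no PFS event count.
- Scan times: week 11, then every 8 weeks. This allows 1 week from randomization to start (Protocol 6.2), 6 weeks of radiotherapy and 4 weeks to the first scan.
- Assumed: exponential time to progression with median 6, 8 or 10 months; each scan missed independently with probability *p* = 5%, 10% or 20%; deaths ignored.
- Counted: progressions detected by week 104, that is, at scans 1 to 12 (weeks 11 to 99).

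**3. Formula.** Let F be the distribution of time to progression, s_j the time of scan j, and s_0 = 0. Progression is detected at scan j with scan j−1 attended and at least two earlier misses with probability

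[F(s_j) − F(s_{j−1})] × (1−p)² × P(Bin(j−2, p) ≥ 2).

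Sum this over j = 2 to 12. Divide by the probability of detection by week 104, which is the sum over i = 1 to 12 of [F(s_i) − F(s_{i−1})] × (1 − p^(13−i)).

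**4. Growth with follow-up, p = 10%.** Among progressions found with the previous scan attended, the share the cumulative rule censors is P(Bin(j−2, 0.1) ≥ 2).
- Week 51 (j = 6, four earlier scans): 1 − 0.9⁴ − 4 × 0.1 × 0.9³ = 1 − 0.6561 − 0.2916 = 5.2%.
- Week 99 (j = 12, ten earlier scans): 1 − 0.9¹⁰ − 10 × 0.1 × 0.9⁹ = 1 − 0.3487 − 0.3874 = 26.4%.

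**5. Worked case, median 8 months, p = 10%.** The weekly rate is ln 2 / (8 × 30.4375 / 7) = 0.0199. The numerator is 0.0327 and the denominator 0.8582, so the share is 3.8%.

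**6. Results.** Share of detected progressions that would be censored although the preceding scheduled scan was attended, over medians of 6 to 10 months:

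| Missed scans | Detected by week 104 | Of these, detected from week 51 |
|---|---|---|
| 5% | 1.0–1.5% | about 3.5% |
| 10% | 3.0–4.4% | 10–11% |
| 20% | 6.8–9.9% | 21–23% |

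Monte Carlo runs of the same set-up agree. Under a rule requiring consecutive misses directly before the event, each of these shares is zero by definition.

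**The case against.** The strongest reply is that the detailed rule already settles the matter. SAP 11.3.1 refers to 15.2 and the Protocol defers to the SAP. A progression found one interval after an adequate scan does not follow a prolonged loss to follow-up. The row on deaths between adequate assessments points the same way. This stands as far as intent goes: 15.2 very probably means a gap. It does not remove the inconsistency. The bracket in 15.2 defines its phrase by the same bare count, no text says that 15.2 overrides 11.3.1, and 11.3.1 states an operative rule of its own.

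Other parts of the reply also stand. All quantities in the size calculation are assumed, and 20% missed scans has no support in the documents. Misses caused by travel restrictions would tend to cluster, which narrows the difference between the two rules. In Appendix L, skipping a scan is the last of four options in order of preference, and the window is widened to 2 weeks, so that section works mainly to prevent misses.

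Three stronger readings are tempting and not supported:
- *That the plan discards progressions found right after an adequate MRI.* This happens only if the cumulative wording is what gets programmed, and the documents do not show that.
- *That the loss equals everything the cumulative count censors.* At 10% missed scans that total is about 7.4–10.0% of progressions by week 104. Of this, 2.0–2.3% would be censored under a gap rule anyway, and another part has one missed scan directly before the event.
- *That the treatment comparison is biased.* The arms may enter the looser post-treatment imaging at different times, but nothing in the documents establishes unequal miss rates or an effect on the hazard ratio.

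**Conclusion.** The point holds as an inconsistency in a stated rule. SAP 11.3.1 and Protocol 7.1.3 count misses over the whole history, SAP 15.2 points to a gap without saying so cleanly, and the same patient can be censored or an event.

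The size is conditional on the cumulative wording being programmed. It is small overall at low miss rates and larger among late progressions, as tabulated, and it rests on the assumed exponential PFS, independent misses and strict 8-week scanning. PFS lies outside the type I error control, OS does not use this rule, and the long-term analysis is descriptive. The correction should nevertheless be made, because the rule as worded gives a wrong answer for identifiable patients and the choice should not be left to programming.

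**What to change.** In SAP 11.3.1 and the last row of SAP 15.2, and in Protocol 7.1.3 if it is amended, replace the rule with:

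> Subjects with two or more consecutive missed scheduled assessments immediately preceding the progression or death, with no adequate assessment in between, are censored at the last adequate assessment before that gap. Isolated missed assessments followed by an adequate progression-free assessment do not lead to censoring.

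Add a definition of a missed assessment, counted against the 8-week schedule and its windows (including the wider pandemic window). State how it applies after treatment, when standard-of-care MRI is accepted; without this, even a consecutive-miss rule cannot be applied uniformly. Confirm that the PFS and response-duration programs follow this rule in both the primary and the long-term analysis.

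The cost is one sentence and one definition. It needs no new data and no added analysis, and censoring after a true gap is unchanged.
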